#### Figure 1. Outline Protocol

##### Initial Steps

1. Informed consent is obtained from eligible patients
2. Observer #1 (not the surgeon) maps the extent of the BCC tumour using OCT. The time taken, size and shape of the mapped border is recorded.
3. The OCT marks are removed and the patient is asked to return at a later date for the surgical procedure
4. Patients are randomized into two groups, A. OCT Arm and B. Control Arm

##### A. OCT Arm

5. Observer #2 (the Mohs surgeon) maps the extent of the BCC tumour using OCT. The time taken, size and shape of the mapped border is recorded.
6. The Mohs surgeon performs Mohs surgery using the marked OCT mapped borders as the first stage estimate. The number of MMS stages is recorded.

##### B. Control Arm

7. Standard Mohs surgery is performed, using clinical assessment for the first MMS stages

##### Final Observations

8. Finally, prior to closure of the wound, the size of the surgical defect of all lesions is measured by tracing the extent on squared transparent paper and also photographed with a scale. The subtype of the BCC from the Mohs histology is recorded (nodular / superficial / infiltrative / other)

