#### Tertiary Objectives:

- For those lesions for which OCT margin mapping did not result in a single stage operation:
  - o Determine the proportion of each BCC subtype (nodular, superficial, or infiltrative BCC)
  - o Determine the proportion for which the first surgery stage had margins that were not clear (i) laterally (ii) in depth
  - o Determine whether anatomical location is a factor

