#### Population:

##### Inclusion criteria:

- 200 patients with biopsy-proven BCCs who have been referred for MMS
- Adults  $> 18$  years of age
- Informed consent

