#### Case Number Estimation:

N=200 patients will be included in the study (100 in each arm).

According to published literature, the average number of MMS stages per lesion is in the range 1.5 to 1.7 [6]. Previous studies with small numbers of patients in non-RCT conditions indicate that presurgical margin mapping with OCT reduces the average number of stages to approximately 1.2 [1-5]. Analysis by a qualified statistician has shown that assuming the true value is 1.2, then 83 patients in the OCT arm will be sufficient to show that the average number of MMS stages is  $< 1.4$  with a confidence level of 95% ( $P < 0.025$ ). This study will be performed with 100 patients in each arm in order to exceed this criterion and show that OCT mapping improves on standard MMS with 1.5 – 1.7 stages.

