### 3. Tertiary Objectives

The results for all lesions in the OCT arm which took more than 1 MMS stage will be analysed as follows:

Calculate the proportions of each BCC subtype (nodular, superficial, or infiltrative BCC, or other) as a % of the total

Calculate the proportion for which the first surgery stage had margins that were not clear (i) laterally (ii) in depth (iii) both

Calculate the proportions of lesions in each of the following anatomical locations: nose, periocular, perioral, ear, other facial location, neck, trunk, limbs.

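### Subtype comes only from Mohs histology and is tabulated only for OCT-arm lesions needing more than one stage, so the table cannot show which subtypes OCT mapping fails on (minor)

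*Protocol*

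**What the plan says.** Final Observations in the Outline Protocol gives the source of subtype: "The subtype of the BCC from the Mohs histology is recorded (nodular / superficial / infiltrative / other". No other source is named anywhere. It does not say which tissue is typed (margin sections only, or debulked central tumour as well) or who does the typing.

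The Inclusion criteria admit "200 patients with biopsy-proven BCCs who have been referred for MMS", so every patient has had a diagnostic biopsy before mapping and randomisation. The protocol does not use it for subtype.

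Subtype has one planned use. The tertiary objective is limited by "For those lesions for which OCT margin mapping did not result in a single stage operation". The matching part of Data and Analysis (3. Tertiary Objectives) begins "The results for all lesions in the OCT arm which took more than 1 MMS stage will be analysed as follows" and then specifies "Calculate the proportions of each BCC subtype (nodular, superficial, or infiltrative BCC, or other) as a % of the total". What the total is, is not defined. No subtype tabulation is planned for single-stage lesions or for the Control Arm.

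**The concern.** A reader of the tertiary table will want to know whether OCT mapping does worse in some subtypes than in others. That is a question about the rate of multi-stage surgery within each subtype. The planned table gives the reverse quantity, the subtype shares among multi-stage lesions. To get from one to the other, the subtypes of the lesions that cleared in one stage are needed. The plan does not tabulate them, and its chosen source may be least able to supply them.

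At stake is how far a descriptive tertiary result can be interpreted. The trial's main conclusions do not depend on it.

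**Working it through.** The protocol states no figure on this point, so there is none to reproduce. The check sizes the two groups of lesions and then asks what the planned table determines.

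**Inputs.** Case Number Estimation gives 100 patients per arm and, for the OCT arm, "presurgical margin mapping with OCT reduces the average number of stages to approximately 1.2".

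**Step 1: lesions in the table.** The number of stages S is an integer of at least 1, so mean(S) − 1 is at least P(S > 1), whatever the distribution. At a mean of 1.2:

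- P(S > 1) ≤ 1.2 − 1 = 0.20, so at most 20 of 100 lesions are in the table.
- P(S = 1) ≥ 1 − 0.20 = 0.80, so at least 80 of 100 are outside it.

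The single-stage share under three models with mean 1.2:

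| Model (assumed) | Formula | Single-stage | Multi-stage of 100 |
|---|---|---|---|
| Never more than two stages | 1 − 0.2 | 0.80 | 20 |
| Extra stages Poisson | exp(−0.2) | 0.82 | 18 |
| Geometric | 1/1.2 | 0.83 | 17 |

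The table would rest on about 17 to 20 lesions.

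**Step 2: what a share among failures determines.** For one subtype, let a be its number of multi-stage lesions and b its number of single-stage lesions. The rate of interest is a/(a + b). The planned table gives a/20 and nothing about b. As an illustration, take a = 10 of 20 (a share of 50%) with 80 single-stage lesions:

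| b (of 80) | Rate in this subtype | Rate in all other subtypes |
|---|---|---|
| 0 | 10/10 = 100% | 10/90 = 11% |
| 40 | 10/50 = 20% | 10/50 = 20% |
| 80 | 10/90 = 11% | 10/10 = 100% |

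The same 50% share fits a subtype that always fails, one that fails like the rest, and one that fails far less often. Reading the total as all OCT-arm lesions gives 10/100 = 10%, which is still not the rate within the subtype.

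**Step 3: where subtype may be unavailable.** The protocol classes first-stage failures by margin: "Calculate the proportion for which the first surgery stage had margins that were not clear (i) laterally (ii) in depth (iii) both". A lesion needing a further stage therefore had tumour visible at a first-stage margin and can be typed. A lesion cleared at stage 1 had none there. If margin sections are all that is typed, b may be partly or wholly unknown for the 80 or more single-stage lesions. If debulked tumour is typed too, the gap largely closes. The protocol settles neither case.

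**The case against.** The strongest reply is that the protocol does what it says. The objective asks only for subtype proportions among lesions that were not single-stage. The language of a factor is attached to anatomical location, not to subtype. Those lesions had visible tumour, so missing subtype among single-stage lesions does not bias the planned proportion. In a mixed tumour, the subtype at the positive margin is arguably the relevant one for why the first stage failed. All of this stands. It limits the point to what the table can be used for and keeps the severity low.

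Four stronger readings are tempting, and the protocol does not support them:

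- **That Mohs histology shows tumour only when a margin is positive, so subtype will be missing in about 80% of the OCT arm.** This needs the assumption that only margin tissue is typed and the worst case that every single-stage lesion is then unreadable. Final Observations makes no exception for single-stage lesions and appears to expect a subtype for all.
- **That an unblinded surgeon assigns the subtype.** The protocol does not say who does.
- **That subtype could not serve to check comparability of the arms.** No such use is planned.
- **That the biopsy should replace Mohs histology.** Each source has a weakness: a small biopsy can miss a mixed or infiltrative component. Nor does the protocol say that the biopsy report states a subtype.

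The small size of the table follows from its restriction to multi-stage lesions, not from the source of subtype. Another source would not enlarge it. With 10 of 20, the exact 95% interval for the share is 27% to 73%.

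**Conclusion.** The point holds as a minor one. The planned table describes at most 20 of 100 OCT-arm lesions at a mean of 1.2 and omits at least 80. It cannot show which subtypes OCT mapping fails on, whatever tissue is typed. That conclusion needs only that stages are whole numbers of at least 1, together with the protocol's own mean and arm size.

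The further point, that Mohs histology may leave the single-stage lesions without a subtype, is conditional on only margin sections being typed. The planned proportion among multi-stage lesions is not biased by it. The primary and secondary objectives and the sample size are unaffected.

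**What to change.** In Final Observations, also record for every lesion the subtype given in the diagnostic biopsy report, where it gives one, alongside the Mohs subtype. State whether debulked tumour is typed or only margin sections.

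In Data and Analysis, 3. Tertiary Objectives, report for each subtype the number of lesions with more than one stage over all OCT-arm lesions of that subtype. Use whichever source is available for all lesions, with the other as a sensitivity check. If the share among multi-stage lesions is kept as well, say what the total is.

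The cost is one extra data item per lesion, taken from a biopsy already done, with no change to sample size or patient procedures. Two limits remain. Some reports may give no subtype. A small biopsy can also miss a mixed or infiltrative component, which is why the Mohs field is kept. Estimates within subtype will still be imprecise, because the number of multi-stage lesions does not change.

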#### Avoiding Bias:

The initial OCT mapping, prior to randomization, by another Observer who is not the surgeon, is to detect any bias on behalf of the surgeon who might consciously or unconsciously increase the size of the excision in the OCT Arm (therefore unnecessarily increasing the amount of healthy tissue excised) in order to reduce the number of MMS stages. This first Observer does not know which Arm the patient will end up in and so will simply do their best to map the tumour as accurately as possible. It is then straightforward to compare their results (size of mapped margins) with the surgeon's to confirm the absence of any bias. Their OCT mapping results will also be compared with the size of the final surgical defect (for all lesions) to confirm that (as in all previous studies) OCT mapped borders are no larger than the final surgical defect by conventional MMS.

#### Case Number Estimation:

N=200 patients will be included in the study (100 in each arm).

According to published literature, the average number of MMS stages per lesion is in the range 1.5 to 1.7 [6]. Previous studies with small numbers of patients in non-RCT conditions indicate that presurgical margin mapping with OCT reduces the average number of stages to approximately 1.2 [1-5]. Analysis by a qualified statistician has shown that assuming the true value is 1.2, then 83 patients in the OCT arm will be sufficient to show that the average number of MMS stages is  $< 1.4$  with a confidence level of 95% ( $P < 0.025$ ). This study will be performed with 100 patients in each arm in order to exceed this criterion and show that OCT mapping improves on standard MMS with 1.5 – 1.7 stages.

#### Termination Criteria:

The patient will be excluded from the study on personal demand (see informed consent).

#### Start and Duration

The study is designed for 2 years starting immediately after approval by ethics committee. Recruitment will be 2 patients per week.

#### Study-related interventions

The OCT device is CE marked and has been on the market in first and second generations since 2011. A methodology for using OCT to map the lesion margins has been developed since 2011 and results published [refs] and then further optimized.

The study involves manual measurement of the lesion at 3 stages (on clinical assessment, after OCT mapping, and after surgery). The measurement procedure is very simple and involves placing transparent squared paper over the lesion and tracing the extent. This procedure is a well-established technique for measuring the extent of wounds

In the OCT arm of the study, the Mohs surgeon will make a first incision using the marked OCT margins as the first estimation of the tumour border.

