##### 2. Secondary Objectives

- The area of lesions will be obtained from the tracings of the mark obtained by placing a transparent TegaDerm™ adhesive dressing over the mark, removing it (with ink transferred) and pasting on to squared graph paper and then counting the number of squares inside the traced borders.

- The area of the surgical defect will be obtained by placing OpSite™ squared adhesive dressing over the defect prior to commencement of repair, using an ink marker to trace the defect on the dressing, and then counting the number of squares inside the traced borders.
  
- The following will be calculated
  - i. The mean, r.m.s. and maximum difference between the area of the OCT map made by Mohs surgeon and the area of the OCT map made by Observer #1, for lesions in the OCT Arm
  - ii. The mean, r.m.s. and maximum difference of the area of the OCT map made by Observer #1 and the area of final surgical lesion in the Control Arm.

From (i) we will quantify the difference between the Mohs surgeon and Observer's OCT mapping, and whether the Mohs surgeon's margins are consistently smaller or larger.

From (ii) we will determine whether the Observer's margins are smaller or larger than the final surgical lesion, and from (i) then show whether the surgeon's margin are expected to be smaller than the final surgical lesion, and by how much.

Figure 2. Schematic of process showing the areas.

Finally, the average time taken to OCT map lesions will be calculated:

- For all lesions
- For lesions, divided into the following subcategories by clinically visible lesion size:
  - o < 2.0 cm^2
  - o 2.0 – 4.0 cm^2
  - o > 4.0 cm^2

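### The bias feared is a larger excision in the OCT Arm, but the listed checks compare drawn maps and Control-Arm defects, so neither would respond to a wider first cut.

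*Protocol*

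**What the plan says.** All in the Protocol:

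- **Avoiding Bias** describes the bias as a surgeon "who might consciously or unconsciously increase the size of the excision in the OCT Arm", removing healthy tissue in order to need fewer stages. The remedy offered is Observer #1's map, made before randomisation: "It is then straightforward to compare their results (size of mapped margins) with the surgeon's to confirm the absence of any bias".
- **Data and Analysis, Secondary Objectives, calculation (i)** takes the area difference between the "OCT map made by Mohs surgeon and the area of the OCT map made by Observer #1, for lesions in the OCT Arm".
- **Calculation (ii)** takes the difference between "the area of the OCT map made by Observer #1 and the area of final surgical lesion in the Control Arm".
- **Avoiding Bias** also gives a second comparison, wider in scope than (ii): "Their OCT mapping results will also be compared with the size of the final surgical defect (for all lesions". Its stated aim is to confirm that mapped borders do not exceed the final defect.
- **Study-related interventions** says that in the OCT arm the surgeon will "make a first incision using the marked OCT margins as the first estimation of the tumour border". The Control Arm proceeds "using clinical assessment for the first MMS stages".
- **Areas measured:** Study-related interventions names three occasions: clinical assessment, after mapping and after surgery. Figure 1 (Final Observations) has the final defect measured for all lesions. The first-stage incision is measured in neither arm.
- **Secondary Objectives** at the front of the protocol include showing that fewer stages do not come with a larger surgical defect.

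**The concern.** The bias concerns where the surgeon cuts; the check concerns where the surgeon draws. In the OCT Arm the same surgeon maps and then operates, knowing the arm. That surgeon can draw a map that agrees with Observer #1's and still cut further outside it than in the Control Arm.

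The primary endpoint is the number of stages, which depends directly on the width of the first cut. If that width differs between arms for reasons other than OCT information, part of a lower stage count reflects more tissue taken at the first pass. Following the plan as written, the trial could then report that bias had been excluded when it had not been examined. The Study Design section says the second observer's map is there to make completely sure that fewer stages were not bought with more tissue; the listed calculations cannot give that assurance.

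**Working it through.** The plan gives no figure for this point, so the first step sets the checks side by side. The second step is an illustration on assumed inputs.

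**1. Does each check respond to a wider OCT-Arm first cut when the map is unchanged?**

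| Check | Compares | Response |
|---|---|---|
| Calculation (i) | Surgeon's map and Observer #1's map, OCT Arm | None: no incision enters it |
| Calculation (ii) | Observer #1's map and final defect, Control Arm | None: no OCT-Arm patient enters it |
| Avoiding Bias condition | Map no larger than final defect | Wrong direction: a wider cut makes it easier to meet |

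The text after (ii) chains (i) to (ii) to predict how the surgeon's margins relate to the final lesion. That chain still contains no OCT-Arm excision.

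**2. How much could extra first-cut width matter?**

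From the protocol (Case Number Estimation): 1.5 to 1.7 stages with standard surgery, about 1.2 with OCT, target below 1.4. The expected reduction is 1.5 − 1.2 = 0.3 to 1.7 − 1.2 = 0.5.

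Assumed, not in the protocol:
- a round 1 cm² lesion, radius r = √(100/π) = 5.64 mm;
- required margin exponential, with probability p of exceeding 2 mm, p = 0.33 or 0.40;
- first cut at m mm, and each later stage 2 mm.

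*Mean stages* = 1 + p^(m/2)/(1 − p).

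- p = 0.33: m = 2 gives 1 + 0.330/0.67 = 1.49; m = 3 gives 1 + 0.1896/0.67 = 1.28.
- p = 0.40: m = 2 gives 1 + 0.400/0.60 = 1.67; m = 3 gives 1 + 0.2530/0.60 = 1.42.

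The two m = 2 values fall within the protocol's 1.5–1.7 after rounding.

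*First-cut area ratio*, 3 mm against 2 mm: (8.64/7.64)² = 1.28.

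*Final-defect ratio.* Let K be the number of later stages and f the fraction of the perimeter they remove. Mean area is proportional to (r + m)² + f·[4(r + m)·E(K) + 4·E(K²)], with E(K) = p^(m/2)/(1 − p) and E(K²) = p^(m/2)(1 + p)/(1 − p)².

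- p = 0.33, f = 1: (74.68 + 9.78 + 2.25)/(58.40 + 15.06 + 3.91) = 86.71/77.37 = 1.12.
- p = 0.33, f = 0.25: 77.69/63.14 = 1.23.
- p = 0.40, f = 1: (74.68 + 14.57 + 3.94)/(58.40 + 20.38 + 6.22) = 93.19/85.00 = 1.10.
- p = 0.40, f = 0.25: 79.31/65.05 = 1.22.

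So the first cut is 28% larger but the final defect only 10–23% larger, because the wider cut avoids later stages that would have enlarged it. Calculation (i) shows a difference of zero.

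**3. What would the whole expected reduction need?** Setting mean stages to 1.2 gives m = 2·ln[0.2(1 − p)]/ln p:

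- p = 0.33: m = 3.63, 1.6 mm extra, first-cut ratio (9.27/7.64)² = 1.47.
- p = 0.40: m = 4.63, 2.6 mm extra, first-cut ratio (10.27/7.64)² = 1.81.

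A second simulated geometry (map radius 4 or 8 mm, mean tumour extension beyond the map 1.5–3 mm, 2 mm full-ring later stages) needed about 1.4–3.8 mm extra to go from 1.5–1.7 to 1.2, with the mean final defect about 14–63% larger.

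**The case against.** **The final defect is measured.** It is recorded in all lesions, defect size is a secondary objective, and Avoiding Bias extends the map-to-defect comparison to every lesion. The harm named is unnecessary loss of healthy tissue, which the final defect captures. A between-arm analysis could also sit in a statistical analysis plan not seen here. This largely stands: the data for a substantial check exist. It does not rescue the checks as listed, because (ii) is confined to the Control Arm and the stated condition cannot flag an over-wide cut. Nor can any later analysis plan recover first-stage incision size, which is not collected.

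**The marked border may be the cut line.** Figure 1 uses the mapped borders as the first-stage estimate, and on that reading (i) compares planned excisions. The wording allows this. But Study-related interventions calls the marks an estimate of where the tumour ends, and on either reading the actual cut is not measured.

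**A wider first cut may be legitimate.** If OCT shows tumour beyond the clinical border, an honest surgeon makes a larger first cut in the OCT Arm; that is how the method would work. This stands and shapes the repair. First-cut area compared between arms, adjusted only for Observer #1's map, would mistake benefit for bias.

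**A reader might infer that a wider cut could explain the whole stage reduction and remain unseen.** The material does not support that. The 1 mm example reaches 1.28–1.42, not 1.2, and its upper case misses the 1.4 target. Reaching 1.2 needs 1.6–2.6 mm in the same model and a first cut 47–81% larger, which would also leave a larger final defect in data the trial already collects.

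**Conclusion.** The point holds in a limited form. The protocol names a bias in the excision and claims to exclude it with a comparison of drawings. Neither listed calculation can respond to a wider OCT-Arm cut, and the remaining condition points the wrong way. Avoiding Bias and calculation (ii) also disagree on whether OCT-Arm defects are included. This follows from the text and needs no modelling assumption.

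The size is not established. That extra width could account for part of the stage reduction is a possibility; nothing in the protocol shows that surgeons will cut wider. The shift of 0.21 (1.49 to 1.28) or 0.25 (1.67 to 1.42) stages per extra millimetre, and the 10–23% larger defect, rest on the assumed lesion size, margin distribution and stage width. This should be corrected, but the trial can run, and most of the remedy uses data already planned.

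**What to change.** 1. **Reconcile Avoiding Bias with calculation (ii)** so that both cover the same lesions. Then compare final defect area between arms, adjusted for Observer #1's pre-randomisation map area. Make this the analysis of the defect-size objective and the main check on excess tissue removal. It needs no new data.
2. **Trace the first-stage incision in both arms** with the dressing method already used for the other areas. Report its area relative to the border the surgeon worked from: the surgeon's OCT map in the OCT Arm, the clinical border in the Control Arm. This separates extra cut width from a border that OCT legitimately moved. The clinical border should be the one used on the day of surgery, so the protocol should say when that tracing is made.
3. **Stop describing map-to-map agreement as confirming unbiased excision.** Keep calculation (i) as a measure of agreement between observers.

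The cost is one short extra tracing per case, one regression, and possibly a repeat tracing of the clinical border in the Control Arm if the existing one is made only at consultation. The sample size is unchanged. No margin width is proposed; that stays with the surgeon.
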